#### 5.2.1. Analyses for Continuous Endpoints

Unless otherwise stated, continuous variables will be presented using summary statistics: number of observations, arithmetic mean, standard deviation, median, minimum and maximum values.

#### 5.2.2. Analyses for Categorical Endpoints

Categorical variables will be presented using summary statistics: number of observations and percentages.

#### 5.2.3. Mixed effects model

A mixed effects model with treatment as a fixed effect and participant as a random effect will be used. *Estimates of the adjusted* (least squares) *mean differences (Test-reference) and corresponding 90% CIs will be obtained from the model. The adjusted mean differences and 90% CIs for the differences will be exponentiated to provide estimates of the ratio of adjusted geometric means (Test/Reference) and 90% CIs for the ratios.* 

> DMB02-GSOP-RF02 7.0 Statistical Analysis Plan Template 31-Jan-2022 PFIZER CONFIDENTIAL TMF Doc ID: 98.03 Page 15 of 30

The mixed effects model will be implemented using SAS Proc Mixed, with REML estimation method and the Kenward-Roger degrees of freedom algorithm.

Residuals from the models will be examined for normality and the presence of outliers via visual inspection of plots of residuals vs predicted values and normal probability plots of residuals but these will not be included in the clinical study report. If there are major deviations from normality or outliers (where studentized [conditional] residuals are greater than 3 or less than -3) then the effect of these on the conclusions may be investigated through alternative transformations and/or analyses excluding outliers. Justification for any alternative to the planned analysis will be given in the report of the study if applicable.

Example code is shown in Appendix 1.

#### 5.3. Methods to Manage Missing Data

For the analysis of safety endpoints, the sponsor data standard rules for imputation will be applied.

In all exploratory safety data presentations (except listings), concentrations below the limit of quantification (BLQ) will be set to the lower limit of quantification (LLOQ).

In all PK data presentations (except listings), concentrations below the limit of quantification (BLQ) will be set to zero. In listings BLQ values will be reported as "<LLOQ", where LLOQ will be replaced with the value for the LLOQ.

In PK summary tables and plots of median profiles, statistics will be calculated having set concentrations to missing if one of the following cases is true:

1. A concentration has been collected as ND (i.e. not done) or NS (i.e. no sample),

2. A deviation in sampling time is of sufficient concern or a concentration has been flagged anomalous by the pharmacokineticist/statistician.

Note that summary statistics will not be presented at a particular time point if more than 50% of the data are missing.

Participants who experience events that may affect their PK profile (e.g., lack of compliance with dosing or vomiting) may be excluded from the PK analysis. At the discretion of the pharmacokineticist a concentration value may also be excluded if the deviation in sampling time is of sufficient concern or if the concentration is anomalous for any other reason.

A full list of protocol deviations will be compiled and reviewed to identify major and minor deviations prior to database closure.

#### 5.3.1. Plasma Pharmacokinetic Parameters

Actual PK sampling times will be used in the derivation of plasma PK parameters.

DMB02-GSOP-RF02 7.0 Statistical Analysis Plan Template 31-Jan-2022 PFIZER CONFIDENTIAL TMF Doc ID: 98.03 Page 16 of 30 If a PK parameter cannot be derived from a participant's concentration data, the parameter will be coded as NC (i.e., not calculated). (Note that NC values will not be generated beyond the day that a participant discontinues.)

In summary tables, statistics will be calculated by setting NC values to missing; and statistics will be presented for a particular treatment group/analyte with  $\geq$ 3 evaluable measurements. For statistical analyses (i.e., mixed effects model), PK parameters coded as NC will also be set to missing; and analyses will not be performed for a particular parameter if more than 50% of the data are NC.

If an individual participant has a known biased estimate of a plasma PK parameter (due, for example, to an unexpected event such as vomiting before all the compound is adequately absorbed in the body, e.g., within 2 times the median  $T_{max}$  after the last dose for the respective treatment), this will be footnoted in summary tables and will not be included in the calculation of summary statistics or statistical analyses.

## 6. ANALYSES AND SUMMARIES

For all presentations, study day will refer to the day within a particular treatment period, unless otherwise specified.

## 6.1. Primary Endpoint(s)

## 6.1.1. AUCinf and AUClast for Total Dabigatran and Rosuvastatin

The PK data for rosuvastatin, total dabigatran, and PF-07081532 will be analyzed and reported separately.

AUCinf and AUClast for total dabigatran and rosuvastatin alone and co-administered with PF-07081532 will be listed, summarized descriptively and analyzed by treatment for participants in the PK Parameter Set (as defined in Section 4). Missing values will be handled as detailed in Section 5.3.

Natural  $log_e$  transformed AUCinf (as data permit), and AUClast of total dabigatran administered without PF-07081532 on Period 1 or coadministered with PF-07081532 in Period 4 and on Period 7 will be analyzed using a mixed effect model as described in Section 5.2.3.

*The 2 test treatments will be 'dabigatran and PF-07081532 80 mg QD' (Period 4) and 'dabigatran and PF-07081532 240 mg QD' (Period 7), which will be reported separately in comparison to the reference treatment of 'dabigatran without PF-07081532' (Period 1).* 

Natural  $log_e$  transformed  $AUC_{inf}$  (as data permit), and  $AUC_{last}$  of rosuvastatin administered alone in Period 2 or coadministered with PF-07081532 on Period 5 and Period 8 will be analyzed and reported separately using the same mixed effect model as described above for total dabigatran. The 2 test treatments will be 'rosuvastatin and PF-07081532 80 mg QD' (Period 5) and 'rosuvastatin and PF-07081532 240 mg QD' (Period 8), which will be

> DMB02-GSOP-RF02 7.0 Statistical Analysis Plan Template 31-Jan-2022 PFIZER CONFIDENTIAL TMF Doc ID: 98.03 Page 17 of 30

reported separately in comparison to the reference treatment of 'rosuvastatin without *PF-07081532'* (*Period 2*).

In the event that participants do not successfully titrate to the target PF-07081532 doses by the end of Periods 3 and/or 6, the related PK parameters for total dabigatran and rosuvastatin in the subsequent periods would not be included in the above models (but may be included in sensitivity analyses described below). Note this implies that evaluable PK parameters for the same participants from at least Period 1 (for total dabigatran) and 2 (for rosuvastatin) would be included in the models.

AUCinf and AUClast will be listed, summarized for each treatment (total dabigatran and rosuvastatin will be reported in separate tables) as specified in the table below:

 Table 7. Summary statistics to be produced for plasma PK Parameters of total dabigatran and rosuvastatin

Parameter	Summary Statistics
AUC last & AUC inf	N, arithmetic mean, median, cv%, standard deviation,
	minimum, maximum, geometric mean and geometric cv%.

Supporting data from the estimation of  $AUC_{inf}$  will be listed by treatment: terminal phase rate constant (kel); goodness of fit statistic from the log-linear regression (r); the percent of  $AUC_{inf}$  based on extrapolation ( $AUC_{extrap\%}$ ); and the first, last, and number of time points used in the estimation of kel. This data may be included in the clinical study report.

As a sensitivity analysis an additional physiologically-based PK or other related model may be explored if fewer than 16 participants have PK parameters as above to further characterize the relationship between PK of PF-07081532 and PK of total dabigatran and/or rosuvastatin, which would be reported outside of the CSR.

The following plots will be presented:

 Box and whisker plots for individual PK parameters (AUCinf and AUClast) will be presented by treatment and overlaid with geometric means. These will be produced for total dabigatran and rosuvastatin PK parameters separately.

The following will additionally be presented for the plasma concentration data of total dabigatran and rosuvastatin (reported in separate tables) using the PK Concentration Set (as defined in Section 4):

- a listing of all concentrations sorted by participant ID and nominal time post-dose for each treatment (i.e. total dabigatran and rosuvastatin dosed alone or co-administered, as applicable) separately. The concentration listing will also include the actual times. Deviations from the nominal time will be given in a separate listing.
- a summary of concentrations by each nominal time post-dose (produced separately for each treatment), where the set of statistics will include n, mean, median, standard deviation, coefficient of variation (cv), minimum, maximum and the number of concentrations above the lower limit of quantification.

DMB02-GSOP-RF02 7.0 Statistical Analysis Plan Template 31-Jan-2022 PFIZER CONFIDENTIAL TMF Doc ID: 98.03 Page 18 of 30

- median concentration time plots (on both linear and semi-log scales) against nominal time post-dose by treatment. Two plots will be presented for each scale: one for the three treatments with total dabigatran and another for the three treatments with rosuvastatin.
- individual concentration time plots by treatment (on both linear and semi-log scales) against actual time post-dose (there will be separate spaghetti plots for each treatment, with a line for each participant per scale). Plots for total dabigatran and rosuvastatin will be produced separately.
- individual concentration time plots by participant (on both linear and semi-log scales) against actual time post-dose. Two plots for each participant and scale will be presented: one for the three treatments with total dabigatran and one for the three treatments with rosuvastatin.

The nominal PK sampling time will be used for summary statistics and relevant median plots, whereas for individual participant plots by time, the actual PK sampling time will be used.

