#### 4.2.2. Collection of Retained Research Samples

#### 4.3. Justification for Dose

PF-07081532: The drug-drug interactions will be assessed at 2 PF-07081532 dose levels, 80 mg QD and 260 mg QD. These doses represent a potential therapeutic dose for T2DM, and the highest dose being assessed in the Phase 2 study (C3991004) for T2DM and obesity, respectively. Exposure margins for the PF-07081532 260 mg QD dose are provided in Section 2.2.3.

The titration to PF-07081532 80 mg QD is planned to occur over an 8-day period in increments of 20 mg to 40 mg QD every 4 days, and from 120 mg QD to 260 mg QD over 20 days, in increments of 20 mg to 40 mg every 4 days (Section 6.1, Table 7). Titration increments as short as 1-2 days have been administered previously in Study C3991002 and were sufficiently tolerated.

Based on emerging data from other clinical studies that may become available during the conduct of this study, the titration rate, incremental increases in dose, and/or the PF-07081532 doses at which rosuvastatin or the dabigatran PK interactions are evaluated may be adjusted. If participants are not able to tolerate titration to higher doses of PF-07081532 (eg, ≥180 mg QD), titration to the next dose level may be delayed temporarily or titration to a maximum tolerated dose may be permitted, with sponsor approval only.

Rosuvastatin: In a single dose escalation study, rosuvastatin was safe and well tolerated at doses up to 80 mg. The most common AEs reported were headache and rash. There was no evidence of a relationship between the frequency of AEs and rosuvastatin dose. No SAEs were reported.

After oral administration of rosuvastatin in healthy participants, Cmax occurred at 3 to 5 hours post dose. Co-administration of rosuvastatin with food had no impact on its exposure. Both Cmax and AUC increased in an approximately dose-proportional manner. The elimination half-life of rosuvastatin is approximately 19 hours. Rosuvastatin is a substrate for certain transporter proteins including the hepatic uptake transporter, OATP1B1, and the efflux transporter, BCRP.

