Dabigatran was well tolerated after administration of single oral doses of 10–400 mg DE to healthy participants. Seven of 40 participants reported an AE, all of which were mild to moderate in severity. The most frequently reported AE was headache, but in no case was this considered related to treatment with the study drug. There were no significant findings in vital signs and ECGs, in particular heart rate and PR interval, nor in safety laboratory assessments. There were no deaths, no SAEs, and no AEs leading to withdrawal during the study.

In a drug interaction study with a single dose of verapamil 120 mg, a strong P-gp inhibitor, the AUC and  $C_{max}$  of dabigatran (150 mg) increased by 143% and 179%, respectively. The treatments in this study were sufficiently well tolerated despite the increase in dabigatran exposures. The 150 mg dabigatran dose chosen for the current study is expected to be well tolerated.

DE is rapidly converted to dabigatran, which is the main moiety detected in the systemic circulation. Preclinical and clinical data suggest that DE, but not dabigatran, is a substrate of P-gp, therefore, changes in dabigatran exposure reflect an alteration in intestinal P-gp function. A single dose of the perpetrator is sufficient to assess changes in P-gp probe drug absorption, as intestinal P-gp appears to have the most significant impact on DDIs. Therefore, DE will be co-administered with the initial dose of 80 mg and 260 mg PF-07081532 in Periods 4 and 7. (PF-07081532 will continue to be dosed for an additional 4 days in each of Periods 4 and 7 to allow steady-state exposures to be achieved prior to co-administration with single-dose rosuvastatin in Periods 5 and 8, respectively.) Additionally, verapamil, a P-gp inhibitor, was shown to increase dabigatran exposures by a greater magnitude when dosed 1 hour prior to DE administration as compared to simultaneous dosing. Therefore, to assess near maximum intestinal exposures, and thus maximal P-gp modulation by PF-07081532, DE will be administered ~60 min following administration of PF-07081532.

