#### Figure 1. Study Design

The total duration of participation from the Screening Visit to the F/U outpatient telephone contact will be approximately 115 days or 16.5 weeks, approximately 8 weeks of which will be conducted on an inpatient basis.

The 54-day inpatient portion of the study will be conducted as follows:

Period 1: 3 days, includes CRU admission on Day -1 (DE 150 mg single dose);

Period 2: 4 days (rosuvastatin 10 mg single dose);

Period 3: 8 days (PF-07081532 titrated to 40 mg QD);

*Period 4: 5 days (DE 150 mg single dose + PF-07081532 80 mg QD);* 

Period 5: 4 days (rosuvastatin 10 mg single dose + PF-07081532 80 mg QD);

*Period 6: 20 days (PF-07081532 titrated to 240 mg QD);* 

*Period 7: 5 days (DE 150 mg single dose + PF-07081532 240 mg QD);* 

Period 8: 5 days, includes discharge day from CRU (rosuvastatin 10 mg single dose + PF-07081532 240 mg QD).

DMB02-GSOP-RF02 7.0 Statistical Analysis Plan Template 31-Jan-2022 PFIZER CONFIDENTIAL TMF Doc ID: 98.03 Page 8 of 30 The onsite F/U visit/telephone F/U contact will occur 7-10 days from the last dose of study intervention (Period 8, Day 4) and an outpatient telephone F/U contact will occur 28-35 days from the last dose of study intervention (Period 8, Day 4).

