#### 5.2. General Methods

Unless otherwise stated, all summaries and plots will be presented by treatment group (equivalent to 'by Period'). The following treatment labels (or similar) will be used, which represent Periods 1 to 8 as:

Period	Treatment Label
1	Dabigatran etexilate 150 mg (Period 1)
2	Rosuvastatin 10 mg (Period 2)
3	PF-07081532 titration up to 40 mg QD (Period 3)
4	PF-07081532 80 mg QD + dabigatran etexilate 150 mg (Period 4)
5	PF-07081532 80 mg QD + rosuvastatin 10 mg (Period 5)
6	PF-07081532 titration up to 240 mg QD (Period 6)
7	PF-07081532 240 mg QD + dabigatran etexilate 150 mg (Period 7)
8	PF-07081532 240 mg QD + rosuvastatin 10 mg (Period 8)

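### The titration rule in SAP 6.1.1 applies to the AUC models but not to the matching Cmax models, and it does not check the PF-07081532 dose taken on the DE or rosuvastatin day

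*SAP*

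**What the plan says.** SAP 6.1.1 models log AUCinf and AUClast of total dabigatran (Periods 1, 4, 7) and rosuvastatin (Periods 2, 5, 8). The test treatments are labelled 80 mg QD and 240 mg QD. It then sets a condition: "In the event that participants do not successfully titrate to the target PF-07081532 doses by the end of Periods 3 and/or 6", the substrate parameters from the periods that follow "would not be included in the above models (but may be included in sensitivity analyses described below". Outside the models these AUCs remain visible. They "will be listed, summarized descriptively and analyzed by treatment for participants in the PK Parameter Set (as defined in Section 4", a set with no dose condition, and under SAP 5.2 "all summaries and plots will be presented by treatment group", which means by period.

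SAP 6.2.2.1 models log Cmax for the same periods under the same labels. It refers to SAP 5.2.3 for the model and SAP 5.3 for missing values, and contains no titration condition.

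On Period 3, SAP 2.3 says "Period 3: 8 days (PF-07081532 titrated to 40 mg QD" and SAP 5.2 uses the label "PF-07081532 titration up to 40 mg QD (Period 3". Protocol 4.3 says that "DE will be co-administered with the initial dose of 80 mg and 260 mg PF-07081532 in Periods 4 and 7"; SAP 2.1 later records a cap at 240 mg. Protocol 6.6 allows a delayed step or a maximum tolerated dose with sponsor approval, so an individual's dose can differ from the period label.

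**The concern.** The ratios will be read as the effect of 80 mg and of 240 mg, so a profile belongs in a labelled comparison only if the participant was on that dose. Two features work against this.

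First, the exclusion covers only the AUC models. AUC and Cmax for one comparison can then rest on different participants, and only Cmax is diluted by lower-dose profiles. Protocol 9.3.3 treats AUCinf, AUClast and Cmax together under one model, so nothing suggests that this split was intended.

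Second, the rule looks at titration status at the end of a titration period, not at the dose taken with the substrate. An off-dose profile that passes the check pulls the labelled ratio toward the lower-dose effect. No planned SAP table would show it: summaries follow the period label, and SAP 6.5.3 marks treatment exposure as not applicable.

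**Working it through.** **Step 1: scope of the rule.**

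| | AUCinf, AUClast (SAP 6.1.1) | Cmax (SAP 6.2.2.1) |
|---|---|---|
| Periods and dose labels | 1/4/7 and 2/5/8; 80 and 240 mg | the same |
| Model | SAP 5.2.3 | SAP 5.2.3 |
| Missing values | SAP 5.3 | SAP 5.3 |
| Titration condition | yes, for the models just described | none |

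Neither 5.2.3 nor 5.3 contains the condition. A participant held at 200 mg at the end of Period 6 is therefore out of the 240 mg AUC models and in the 240 mg Cmax model.

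**Step 2: what the check sees.** Protocol Table 8 by study day:

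- Day 14 (end of Period 3): 40 mg.
- Day 15 (DE): 80 mg, the first such dose. Day 20 (rosuvastatin): 80 mg.
- Day 43 (end of Period 6): 240 mg.
- Days 44 (DE) and 49 (rosuvastatin): 260 mg in the protocol, 240 mg in the SAP labels.

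The period lengths 3+4+8+5+4+20+5+5 = 54 reproduce the stated inpatient stay. SAP 2.1 says the executed study was 6 days shorter, so the later days are planned days only. At the end of Period 3 the check falls at 40 mg, one day before the first 80 mg dose. At the end of Period 6 it falls at the labelled 240 mg and misses only a later change.

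**Step 3: other exclusion routes.** SAP 5.3 allows, but does not require, exclusion for events such as dosing non-compliance. SAP 5.3.1 requires exclusion of a known biased estimate, with early vomiting as its example. Neither clearly covers a valid profile at a sponsor-approved lower dose.

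**Step 4: size.** The plan's own precision figures (Protocol Table 13) and the SDs are redacted and cannot be reproduced. The documents give no off-dose count. Everything below is assumed: n = 16, true ratio R = 1.5 at the labelled dose, m profiles off-dose in one test period with true ratio r.

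Expected ratio = exp{[(16 − m) ln R + m ln r] / 16}

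| Lower-dose effect | r | m = 1 | m = 2 | m = 4 |
|---|---|---|---|---|
| none | 1.00 | 1.46 | 1.43 | 1.36 |
| 40 for 80 mg, log effect proportional to dose | 1.5^(40/80) = 1.22 | 1.48 | 1.46 | 1.43 |
| 200 for 240 mg, log effect proportional to dose | 1.5^(200/240) = 1.40 | 1.49 | 1.49 | 1.47 |

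Example, m = 2 and r = 1.00: 14 × 0.4055 / 16 = 0.3548, and exp(0.3548) = 1.43. With R = 1.25 and m = 2 the range is 1.22 (no lower-dose effect) to 1.24 (200 for 240 mg). With R = r = 1 there is no shift.

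The 90% CI half-width on the log scale is t(0.95, 30) × SD × √(2/16), which is 0.120 at a within-participant SD of 0.20 and 0.240 at 0.40. For m = 2 and R = 1.5:

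- No lower-dose effect: shift (2/16) × ln 1.5 = 0.0507, or 42% to 21% of the half-width.
- 200 for 240 mg: shift 0.0507 / 6 = 0.0084, or 7% to 4%.

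**Step 5: cost of exclusion.** The variance of the contrast in the three-treatment model with random participant, times the t quantile, was compared with complete data (within SD 0.20–0.40, between SD 0.3–0.7). Removing 2 of 16 profiles from one test period widens the log-scale 90% CI by 4.7–5.4%. Removing both test periods of those participants widens it by 5.3–7.2%. Removing the participants wholly widens it by 7.4%.

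**The case against.** The case for leaving the text alone has weight.

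- The target doses can be read as the labelled doses, so that the rule means completing the titration into 80 mg. The documents are loose at period boundaries: the protocol describes Period 6 as titrated to 260 mg, while Table 8 ends it at 240 mg. The 40 mg reading is the natural one but not the only one.
- Few cases should fall in the 80 mg gap. Dosing is inpatient and witnessed (Protocol 6.5), departures need sponsor approval, and the examples of intolerance are at 180 mg or above (Protocol 6.6) and 200 mg or above (Protocol 7.1.2).
- At 240 mg the rule already removes from the AUC models anyone still short of the dose at the end of Period 6.
- SAP 5.3 requires deviations to be reviewed before database closure, and its exclusion route covers Cmax. PF-07081532 AUC24 and Cmax are listed for Days 19 and 48, which gives some individual exposure evidence.
- There is no hypothesis test, and Cmax is secondary.

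All of this stands and limits the size. It does not supply the missing condition for Cmax or a dose criterion.

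A reader might also infer two further errors that the documents do not support. Protocol 4.3 says "The titration to PF-07081532 80 mg QD is planned to occur over an 8-day period", which may look like a conflict with Table 8. However, 20 mg and then 40 mg over 8 days, with 80 mg starting when they end, satisfies both. And a participant who first reaches 240 mg on the DE day is excluded even though Protocol 4.3 regards a single perpetrator dose as enough for the P-gp probe. That is a conservative choice, not an error.

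**Conclusion.** The inconsistency between AUC and Cmax is plain on the text. The reliance on end-of-period titration status is a real but narrower weakness: for 80 mg it depends on the natural reading, and for 240 mg it misses only later changes.

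The size is minor and unknown. The SAP version history says that sufficient participants reached 240 mg. This gives no count and does not say that all did, so the case may have occurred but its frequency cannot be stated. Nor do the documents support concluding that the 80 mg results are contaminated, or that dilution reaches 1.43. That value needs 2 of 16 profiles off-dose, a true ratio of 1.5 and no effect at all at the lower dose. With 200 mg taken instead of 240 mg and a log effect proportional to dose, the value is about 1.49. If the true AUC and Cmax ratios are both 1.5 and the 2 profiles are dropped for AUC only, AUC centres on 1.50 and Cmax on 1.43 to 1.49. Protocol 2.2.2 reports that the mechanistic model predicted no clinically relevant transporter interaction; with no interaction there is no shift.

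**What to change.** 1. Replace the titration condition with one inclusion rule: a period's AUC and Cmax both enter a dose-labelled comparison only if the PF-07081532 dose recorded in the CRF on the DE or rosuvastatin day was the labelled dose. For rosuvastatin, also require it on the lead-in days, because Protocol 4.3 intends steady state. Name those days from the executed schedule, since SAP 2.1 says the design in 2.3 is not current.
2. State that the rule governs both SAP 6.1.1 and 6.2.2.1. If the sponsor prefers to keep a stricter titration condition as well, it should apply to AUC and Cmax alike.
3. Report in the CSR the number of participants by actual PF-07081532 dose on each DE and rosuvastatin day.

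The cost is one or two sentences of SAP text and one count table, from doses that Protocol 6.5 already has recorded in the CRF. A few profiles may leave a labelled comparison, with the loss of precision shown in Step 5. If nobody was off-dose, the results do not change and the table shows it.
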